5.1 Primary Endpoint

- 1) The primary efficacy endpoint is the change in Urticaria Control Test (UCT) for each population (CSU-XN, CSU-XF, UF, and CholU). The UCT is a score for symptom control in chronic urticaria, from Day 1 (baseline) to Week 10 for subjects enrolled under Protocol Amendment 2.1 and Week 22 for all remaining subjects (i.e., those on study during Protocol Amendment 3). A change of the UCT score of 3 or more points is regarded as clinically relevant (minimal clinically important difference [MCID]). If Week 10 or Week 22 measures

are not available, they will be imputed with last observation carried forward method (LOCF). The data summary will include Week 10 and Week 22 derived from the available data and Week 10/LOCF and Week 22/LOCF derived from the available plus the imputed data.

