5.2 Secondary Endpoints

- 1) Proportion of subjects with CR, CMR, and DC based on UCT (all patients) at all time points. Section 4 provides the definition of CR, CMR, and DC.
- 2) Change from baseline in disease activity as assessed by UAS7 at each week in CSU patients. If Week 10 or Week 22 measures are not available, they will be imputed with the last non-missing weekly UAS7 (LOCF). The data summary will include Week 10 and Week 22 derived from the available data and Week 10/LOCF and Week 22/LOCF from the available plus the imputed data.

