5.3 Exploratory Endpoints

- 1) Change in [REDACTED] assessed by [REDACTED] [REDACTED] at all post-baseline scheduled visits.
- 2) Proportion of CSU subjects with [REDACTED] each week.
- 3) Proportion of CSU subjects with [REDACTED] from Baseline in [REDACTED] at each week.
- 4) Proportion of CSU subjects with [REDACTED] from Baseline in [REDACTED] at each week.
- 5) Change from baseline in [REDACTED] as assessed by [REDACTED] at each week in CholU patients.
- 6) Change in weekly [REDACTED] over time.
- 7) Change in [REDACTED] at all post-baseline scheduled visits.

For weekly assessment, missing Week 10 and Week 22 scores will be imputed with LOCF.

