6.1 General Methodology

All statistical analyses will be conducted using SAS Version 9.4 or later on the Microsoft® Windows Operating System.

Continuous data will be summarized using n (number of subjects with non-missing observations), mean, median, standard deviation (SD), minimum value, and maximum value. Categorical data will be summarized using the frequency count and percentage (n, %) of subjects in each category. Number of subjects with non-missing values and number of subjects with missing values (e.g., Not Done) will be presented, where appropriate. Subjects with missing values will not contribute to the denominator of percentage calculations. Counts of zero in any category will be presented without percentage.

All endpoints will be summarized by the individual applicable cohorts (CholU, UF, CSU-XN or CSU-XF). Where appropriate, the summaries will also be carried out for all 4 cohorts combined.

Two-sided 95% confidence interval (CI) may be presented for the mean or percentage.

The precision rules for the presentation of summary statistics will be:

- Sample size (n, N) and number of missing responses (if displayed) – Integer
- Mean, CI – One more decimal place than reported/collected
- Standard deviation – Two more decimal places than reported/collected
- Median, other percentile, minimum, maximum – Same number of decimal places as reported/collected
- Ratio – two decimal places
- Percentage – one decimal place generally, or two decimal places for <0.1%

The data summaries will be accompanied by individual subject data listings. All data available from diary, questionnaires, eCRF, and external transfer (e.g., labs) will be listed and will include relevant and pertinent subject information, e.g. study day. The listings will be sorted in the order of Cohort and unique subject ID, and assessment name and assessment date/time.

Dates will be presented in the ISO-8601 format YYYY-MM-DD. Times will be displayed in 24-hour clock format. Numbering for tables, figures and listings will follow ICH E3 Guidelines ([ICH, 1996](#)).

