7.7.1.3 Secondary Efficacy Analyses

All summaries will be provided for each cohort.

- 1) Subjects achieving UCT CR and CMR will be tabulated with % of subjects for each visit. Subjects achieving a maximum of 0, 1, 2, 3, or 4 responses over the 8 post-baseline visits (subjects enrolled under Protocol Amendment 3) will also be tabulated. A 95% CI for the % responses will be calculated using the binomial distribution. Subjects achieving UCT DC will be similarly summarized.
- 2) Changes from baseline in UAS7 in CSU patients will be summarized similarly for each week the diary is collected. A 95% CI for the mean change will be reported. This analysis will also be carried out in the subgroup of CSU-XN patients with baseline UAS7 ≥ 16 .

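### The SAP does not say how a missing endpoint-visit UCT enters the CR, CMR and DC rates; under its general rule, subjects withdrawn for lack of efficacy leave the denominator

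*SAP*

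**What the plan says.** SAP 6.1 has one general rule for percentages: "Subjects with missing values will not contribute to the denominator of percentage calculations". The sentence before it reads: "Number of subjects with non-missing values and number of subjects with missing values (e.g., Not Done) will be presented, where appropriate".

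The rates at issue are the first secondary endpoint in SAP 5.2: "Proportion of subjects with CR, CMR, and DC based on UCT (all patients) at all time points". SAP Section 4 defines all three from the UCT total: CMR is a gain of at least 3 points, DC a score of at least 12, and CR both together. The analysis is in SAP 7.7.1.3 item 1: "Subjects achieving UCT CR and CMR will be tabulated with % of subjects for each visit". Binomial 95% intervals are added, and DC is handled in the same way. Neither place says what happens to a subject whose score is missing.

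Carry-forward is written in three nearby places:

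- SAP 5.1, change in UCT. For missing Week 10 or Week 22 values, "they will be imputed with last observation carried forward method (LOCF"). Summaries are due both with and without the imputed values.
- SAP 5.2 item 2, change in UAS7: "they will be imputed with the last non-missing weekly UAS7 (LOCF").
- SAP 5.3, exploratory endpoints: "For weekly assessment, missing Week 10 and Week 22 scores will be imputed with LOCF".

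SAP 6.4, the section on dropouts and missing data, covers scaling of item and diary scores and incomplete adverse event and medication dates. It does not cover a missed UCT visit.

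**The concern.** Missingness at the endpoint visit can depend on outcome. Protocol 9.4 names lack of efficacy among the grounds for withdrawal. The early-termination assessments share the Week 28 column of protocol Table 3, and SAP 6.2 uses no visit windows, so an early-termination UCT does not stand in for the Week 22 value. A subject who fails and leaves at Week 12, say, contributes to the earlier rates but not to the Week 22 rate.

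There is no control arm, so no comparison rate shifts with it, and with about 12 subjects per cohort one or two exits are enough to move a percentage visibly. Replacement under protocol 9.5 can also make the Week 22 count look complete. What is at stake is how the Week 22 CR, CMR and DC rates and their intervals are read when a later study is considered.

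The study is also open-label. Available-case, carry-forward and non-responder handling can give three different rates from the same data, so the choice is better fixed before results are known.

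**Working it through.** **Inputs.** Cohort size N = 12 and total 48 (SAP 3.3 and 3.6); the one figure the plan allows to be reproduced is 4 × 12 = 48, which agrees. The documents give no dropout rate and no expected response rate. The number of leavers k, the observed responders r, and the number s of leavers who would have responded are therefore assumptions, shown as ranges. N is strictly the number due at that endpoint visit, which can be below 12 because Amendment 2.1 subjects are assessed at Week 10.

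**Formulas.** The available-case rate (SAP 6.1) is r/(N-k). The rate had everyone been observed is (r+s)/N. Their ratio is

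N × r / [(N-k) × (r+s)].

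With s = 0 (every leaver a non-responder) this is N/(N-k): 12/11 = 1.09, 12/10 = 1.20, 12/9 = 1.33. For all cohorts combined, 48/47 = 1.02 and 48/44 = 1.09.

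**Size with N = 12, s = 0.** Intervals are exact (Clopper-Pearson) 95% for r = 6.

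| k | Factor | r = 3 | r = 6 (95% CI) | r = 9 |
|---|---|---|---|---|
| 0 | 1.00 | 25.0% | 50.0% (21.1 to 78.9) | 75.0% |
| 1 | 1.09 | 27.3% | 54.5% (23.4 to 83.3) | 81.8% |
| 2 | 1.20 | 30.0% | 60.0% (26.2 to 87.8) | 90.0% |
| 3 | 1.33 | 33.3% | 66.7% (29.9 to 92.5) | 100.0% |

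**When some leavers would have responded.** Take N = 12, k = 2, r = 6, so the available-case rate is 6/10 = 60.0%.

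| s | Full-data rate | Ratio |
|---|---|---|
| 0 | 6/12 = 50.0% | 1.20 |
| 1 | 7/12 = 58.3% | 1.03 |
| 2 | 8/12 = 66.7% | 0.90 |

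The ratio exceeds 1 exactly when s/k < r/(N-k), that is, when leavers respond less often than those who stay.

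**Opposite error of counting missing as non-response.** With a true rate of 50% and m of 12 missing for unrelated reasons, the expected rate is 0.5 × (12-m)/12: 45.8%, 41.7% and 37.5% for m = 1, 2, 3.

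**Bracketing.** r/N ≤ (r+s)/N always, and (r+s)/N ≤ r/(N-k) whenever s/k ≤ r/(N-k). Shown together, the non-responder and available-case rates enclose the full-data rate as long as leavers respond no better than stayers.

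**The case against.** The strongest reply is that carry-forward already covers this. SAP 5.1 imputes the missing Week 10 or Week 22 UCT and asks for summaries with that imputation; CR, CMR and DC are functions of the same score. In SAP 5.3 the carry-forward sentence covers weekly scores, and some endpoints listed there are themselves responder proportions, so deriving a proportion from an imputed score fits the plan's practice. UAS7 needed its own sentence because it is a different instrument, so silence in 5.2 item 1 is weak evidence that carry-forward was excluded. On this reading every MITT subject due at the endpoint visit has a value and the factor is 1.

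This stands as a plausible reading, and a reader should not infer that the SAP rules carry-forward out. But SAP 5.1 reports Week 22 both ways without saying which feeds the response rates, and carry-forward may count an earlier response as a Week 22 response.

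The plan also offers partial safeguards. Missing counts are shown where appropriate, subject listings and disposition by cohort are required, and for Amendment 3 subjects SAP 7.7.1.3 tabulates "Subjects achieving a maximum of 0, 1, 2, 3, or 4 responses over the 8 post-baseline visits", which can count an early failure under 0. With about 12 subjects per cohort, a careful reader could recompute r/N. These reduce the opacity but do not settle which Week 22 rate is the main one.

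Finally, counting missing as non-response at every visit would turn a continuing responder with one missed visit, or one blank item (SAP 3.8.1 then gives no total), into a failure. That is fair, and is why the change below is limited to the endpoint visit.

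**Conclusion.** The gap is real but modest. SAP 6.1 is a stated available-case rule, and nothing says that the UCT CR, CMR and DC rates use another. Read as written, failures who leave before Week 22 (Week 10 under Amendment 2.1) raise those rates by N/(N-k), provided that every leaver is a non-responder.

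A reader might infer that the plan's rates will be inflated by 9 to 33%. The documents do not support that: they give neither k nor a response rate, the factor drops to 1.03 or 0.90 in the mixed cases above, and there is no effect if nobody leaves. The intervals in the table overlap widely. Nor does the point reach the primary analysis, since the Week 22/LOCF mean change keeps early leavers in. It is not an error-rate problem either, because SAP 3.5 plans no hypothesis tests.

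This is a cheap improvement to a descriptive secondary rate in an open-label pilot.

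**What to change.** In SAP 7.7.1.3 item 1, add:

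> For UCT CR, CMR and DC at Week 22 (Week 10 for Amendment 2.1 subjects), the denominator is all MITT subjects of the cohort assigned that endpoint visit under Section 5.1, including any later replaced under protocol Section 9.5. A subject without a UCT total score at that visit counts as a non-responder. The available-data rate and the rate derived from the LOCF score are shown beside it. Other visits use available data, with the number missing displayed.

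In SAP 6.1, begin the denominator sentence with *Unless specified otherwise*. Tying the assignment to SAP 5.1 matters because SAP 7.7.1 describes the Amendment 3 group a little differently.

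The cost is a few SAP sentences and two extra columns at one visit; no new data and no protocol change. The main rate becomes conservative for subjects missing for reasons unrelated to efficacy, including a single blank UCT item, and the rates beside it show how much that matters. MITT still omits anyone with no post-baseline UCT, so a failure who leaves that early is not recovered.

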6.2 Visit Window and Unscheduled Assessments

There is no visit window for the by visit analysis. Data will be analyzed according to the visit they are associated with.

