## 6. Investigational Plan

### 6.1 Study Design

The study comprises a screening period of 4 weeks, with daily oral intake of standard-dose (once daily) second-generation AH (standard of care, with on-demand intake of up to 3 additional AH tablets per day). The treatment period comprises a daily oral intake of standard-dose second-generation AH and AK002 administered by IV infusion at Days 1, 29, 57, 85, 113, and 141.

Subjects will be followed for an additional 8 weeks, and at Weeks 22, 24, and 28 the primary and secondary objectives will be evaluated.

It is expected that approximately 48 subjects will be enrolled and assigned to 3 cohorts:

- Approximately 12 subjects with Cholinergic Urticaria (CholU)
- Approximately 12 subjects with Urticaria Factitia (UF)
- Approximately 12 XOLAIR® (omalizumab) naïve subjects with Chronic spontaneous urticaria (CSU)
- Approximately 12 subjects with Chronic spontaneous urticaria (CSU) who did not achieve an adequate response to XOLAIR® (omalizumab) in the opinion of the Investigator

The open-label design facilitates the assessment of efficacy, as well as safety in the cohort.

Table 1 shows the study outline and Table 3 shows the schedule of assessments.

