## **9. Discontinuation and Replacement of Subjects and Major Protocol Deviations**

### **9.1 Definition of Early Termination from the Study**

A patient who discontinues the study before completing the Follow-Up visit at Week 28 is considered to have terminated early. All subjects who discontinue the study prior to completing the final Follow-Up visit should return to the site 28 ( $\pm 2$ ) days after the last dose of study drug or prior to this if necessary. If early termination occurs more than 28 days after the last dose of study drug, then perform the Early Termination Visit as soon as possible.

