### **9.3 Early Discontinuation of Study Drug**

A patient may be discontinued from study treatment at any time if the patient, the Investigator, or the Sponsor feels that it is not in the patient's best interest to continue to participate in the study. The following is a list of possible reasons for study treatment discontinuation:

- Patient withdrawal of consent
- AE that, in the opinion of the Investigator, results in it being in the best interest of the patient to discontinue study treatment
- Protocol deviation requiring discontinuation of study treatment

If a patient is withdrawn from treatment due to an AE, the patient will be followed by the Investigator as noted in Section 9.4.

All subjects who discontinue study treatment should return to the site 28 ( $\pm 2$ ) days after the last dose of study drug for procedures listed under Post-Treatment Follow-Up.

All subjects are free to withdraw from participation at any time, for any reason, specified or unspecified, and without prejudice.

Reasonable attempts will be made by the Investigator to provide reasons for patient withdrawals. The reason for the patient's withdrawal from the study will be specified in the patient's source documents.

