## **10. Visit Schedule and Assessments**

[Table 3](#) shows the schedule of assessments by study visit. Subjects should be seen for all visits on the designated day or as close to it as possible.

Subjects discontinuing the study drug before completing the 12-week treatment period, and those who prematurely withdraw from the study for any reason, should be scheduled for an early termination visit as soon as possible, at which time all of the assessments listed for the final visit will be performed.

Subjects who discontinue AK002 treatment also should return for the final assessments. If they refuse to return or are unable to do so, every effort should be made to contact them or a knowledgeable informant by telephone to determine the use of rescue medication and to complete the [REDACTED].

At a minimum, they will be contacted for safety evaluations during the 28 days following the last dose of AK002, including the final contact at the 28-day point. Documentation of attempts to contact the patient should be recorded in the patient record.

All data obtained from the assessments listed in Table 3 and described in detail in the protocol must be supported in the patient's source documentation.

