### **10.5.7.4 PK Analysis**

PK will be analyzed retroactively if possible, using back up blood samples at the following timepoints- before the first dose at Day 1 (Visit 2), Day 29 (Visit 3), Day 85 (Visit 5), Day 155 (Visit 8), and Day 197 (Visit 10)/End or Study/Early Termination).

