3.1 General Description

This is an open-label, pilot study to assess the efficacy and safety of AK002 in subjects with antihistamine-resistant chronic urticaria. The study comprises a screening period of 4 weeks, with daily oral intake of standard-dose (once daily) second-generation antihistamine (AH) (standard of care, with on-demand intake of up to 3 additional AH tablets per day). The treatment period comprises a daily oral intake of standard-dose second-generation AH and AK002 administered by IV infusion at Days 1, 29, 57, 85, 113, and 141. The primary and secondary endpoints will be evaluated at Week 10, 2 weeks after last dose, for subjects enrolled under Protocol Amendment 2.1 and Week 22, 2 weeks after last dose, for all remaining subjects (i.e., those on study during Protocol Amendment 3), and then patients will be followed for an additional 4 weeks (Week 24). The study design is presented schematically in [Table 1](#).

Table 1 Schedule of Assessments for the Main Study

Description	Visit 1	Visit 2	Visit 3	Visit 4	Visits 5, 6, 7	Visit 8	Visit 9	Visit 10
	Day -28	Day 1	Day 29 (± 2)	Day 57 (± 2)	Days 85, 113, and 141 (± 2)	Day 155 (± 2)	Day 169 (± 2)	Day 197 (± 2)
	Week -4	Week 0	Week 4	Week 8	Weeks 12, 16, and 20	Week 22	Week 24	Week 28
	Screening	Baseline/Dosing	Dosing	Dosing	Dosing ^r	Response Assessment ^t	Response Assessment	End of Study/ Early Term.
Informed consent	x ^a							
Eligibility assessment/ confirmation	x	x ^b						
Demographic data	x							
Medical history	x							
Prior CU treatment	x							
Prior/concomitant medication	x	x	x	x	x	x	x	x
Rescue medication use		x	x	x	x	x	x	x
Study Drug administration ^c		x	x	x	x			
Patient diary ^{d,s}	x	x	x	x	x	x	x	x
UAS7		x	x	x	x	x	x	x
		x	x	x	x	x	x	x
		x	x	x	x	x	x	x
UCT		x	x	x	x	x	x	x
q	x	x	x	x	x	x	x	x
		x	x	x	x	x	x	x
		x	x	x	x	x	x	x
		x	x	x	x	x	x	x
and FricTest® ^e	x (if applicable)	x (if applicable)	x (if applicable)	x (if applicable)				
Skin biopsy ^p		x				x		

Table 1 Scheduled of Assessments (continued)

Description	Visit 1	Visit 2	Visit 3	Visit 4	Visits 5, 6, 7	Visit 8	Visit 9	Visit 10
	Day -28	Day 1	Day 29 (± 2)	Day 57 (± 2)	Days 85, 113, and 141 (± 2)	Day 155 (± 2)	Day 169 (± 2)	Day 197 (± 2)
	Week -4	Week 0	Week 4	Week 8	Weeks 12, 16, and 20	Week 22	Week 24	Week 28
	Screening	Baseline/Dosing	Dosing	Dosing	Dosing ^r	Response Assessment ^t	Response Assessment	End of Study/ Early Term.
Anti-drug antibodies ^f		x	x		x	x		x
PK analysis ^f		x	x		x	x		x
Blood safety ^g	x	x	x	x	x	x	x	x

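### Read literally, SAP 6.2 files early-termination UCT scores under Week 28, and SAP 5.1 leaves open whether they feed the Week 22 LOCF

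*SAP*

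**What the plan says.** **Placing data in time.** SAP 6.2, whose title covers visit windows and unscheduled assessments, says: "There is no visit window for the by visit analysis. Data will be analyzed according to the visit they are associated with". It gives no rule for ET or unscheduled values.

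**Where ET sits.** In SAP Table 1 (Section 3.1) and Protocol Table 3, the Visit 10 / Day 197 / Week 28 column is headed "End of Study/ Early Term". No other column mentions ET. Protocol 10.5.7.4 joins the same items in its sampling list: "and Day 197 (Visit 10)/End or Study/Early Termination".

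**What is done at ET.** Protocol Section 10 calls for an ET visit "at which time all of the assessments listed for the final visit will be performed". UCT is one of those assessments.

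**When ET happens.** Protocol 9.1: "All subjects who discontinue the study prior to completing the final Follow-Up visit should return to the site 28" (±2) days after the last dose. The visit may be earlier if needed, or as soon as possible when termination comes later than that. Under Protocol 9.3, subjects who stop study drug also return 28 (±2) "days after the last dose of study drug for procedures listed under Post-Treatment Follow-Up".

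**How the data are used.** SAP 5.1 sets the primary timepoint at Week 22 (Week 10 for Amendment 2.1 subjects) and imputes a missing value by LOCF, reporting observed and LOCF results side by side. SAP 6.4 covers dropouts in its title, but its text deals with score scaling and incomplete dates. SAP 7.7.1 summarises UCT at Week 28 for subjects enrolled after Amendment 3, and at no visit beyond Week 16 for Amendment 2.1 subjects. SAP 7.1.1 admits to MITT any dosed subject with one post-baseline UCT.

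**The concern.** An ET visit can fall at almost any time after the first dose, yet the schedule gives it only one label, and that label is eight weeks after the sixth infusion. With no windows to correct this, the Week 28 summary would combine subjects who completed treatment and follow-up with subjects last seen months earlier after fewer doses. The mean would move towards the ET scores. If people leave because they are not doing well (lack of efficacy is a listed withdrawal reason in Protocol 9.4), it would move down.

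The label may also affect the primary timepoint. A score filed under Week 28 comes after Week 22 in visit order, although by date it may come well before. Whether it is carried forward depends on an ordering that the SAP does not state. SAP Section 9 requires independently programmed datasets to match fully. Two programmers could each follow the SAP and still produce different Week 22/LOCF values.

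**Working it through.** The plan has no power calculation, hypothesis test or dropout rate, so there is no figure of its own to reproduce. The check is day arithmetic followed by an illustration of size.

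**1. Nominal ET day.** Inputs: study drug is "administered by IV infusion at Days 1, 29, 57, 85, 113, and 141" (Protocol 6.1), and ET is 28 (±2) days after the last dose (Protocol 9.1). Formulas: ET day = last dose day + 28; gap to Week 28 = 197 − ET day.

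| Last dose | Dose day | ET day | Gap to Day 197 | Before Week 22 (Day 155 ± 2)? |
|---|---|---|---|---|
| 1 | 1 | 29 | 168 d (24 wk) | yes |
| 2 | 29 | 57 | 140 d (20 wk) | yes |
| 3 | 57 | 85 | 112 d (16 wk) | yes |
| 4 | 85 | 113 | 84 d (12 wk) | yes |
| 5 | 113 | 141 | 56 d (8 wk) | yes |
| 6 | 141 | 169 | 28 d (4 wk) | no |

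After doses 1 to 5 the ET day coincides with scheduled Visits 3 to 7, and after dose 6 with Visit 9. A natural analysis visit therefore exists in every case.

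**2. Effect on the Week 28 mean (assumed inputs).** Take a cohort of 12 (Protocol 6.1), k early terminators with UCT change 0, and 12 − k completers with change c. Then mean = (12 − k) × c / 12.

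- c = 3: k = 1 gives 33/12 = 2.75; k = 3 gives 27/12 = 2.25. Completers alone give 3.
- c = 6: k = 1 gives 66/12 = 5.5; k = 3 gives 54/12 = 4.5. Completers alone give 6.

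**3. Effect on Week 22/LOCF.** For a subject who stops after doses 1 to 5 and has no Week 22 UCT:

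- LOCF by date carries forward the ET score, because it is the latest one before Day 155.
- LOCF by nominal visit order treats the ET score as Week 28, skips it and uses the previous scheduled score.

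If the two scores differ by d points, the cohort mean differs between the readings by k × d / 12. For k = 1, d = 3 this is 3/12 = 0.25. For k = 2, d = 6 it is 12/12 = 1.0. For k = 3, d = 6 it is 18/12 = 1.5.

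**4. A case that falls through.** A subject who receives only dose 1 and returns on Day 29 as an ET visit has a baseline UCT and one post-baseline UCT, the ET score. That subject enters MITT under SAP 7.1.1. If LOCF runs by visit order, there is no Week 22/LOCF value for that subject.

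**5. What is not affected.** UAS7 LOCF uses the last non-missing weekly diary score (SAP 5.2), so it depends little on the ET visit label.

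**The case against.** The strongest reply is that the shared column only lists which assessments are done, and that the eCRF may carry its own ET label. Protocol Sections 9.1, 11, 11.4 and 11.6.1 speak of early termination or its visit separately from Day 197 or the end of follow-up. With such a label, ET data would not be associated with Week 28. This cannot be settled from the documents, so the Week 28 placement is the literal reading and not a certainty. A separate label would not close the gap, however: the ET score would then belong to none of the weeks listed in SAP 7.7.1, and its role in LOCF would still be undefined.

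A reader might go further and infer that the SAP excludes ET scores from the Week 22 LOCF and so favours the drug. The documents do not support that. SAP 6.2 governs the by-visit analysis, while LOCF is set in SAP 5.1, which neither orders observations by visit number nor bars ET values. Taken by date, which is the ordinary meaning of last observation, a pre-Week 22 ET score is carried forward. Nor is the direction one-sided: low ET scores pooled into Week 28 count against the drug.

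Three limits also stand. After dose 6 the ET score falls on Day 169, so leaving it out of the Week 22 LOCF is correct. The Week 28 problem does not reach Amendment 2.1 subjects, whose summaries end at Week 16. And Week 28 is not a designated relapse endpoint: Protocol 5.2 puts relapse and sustained effect at Visit 7, and the SAP lists no relapse endpoint.

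**Conclusion.** The point holds in two parts of different strength. First, on the literal reading of SAP 6.2 with the schedules, ET UCT scores from subjects on the Amendment 3 onward schedule who leave after doses 1 to 5 are reported at Week 28, which is 8 to 24 weeks after their nominal date. This assumes that the eCRF has no separate ET visit label. Second, SAP 5.1 does not say whether LOCF for Week 10 or Week 22 runs by date or by visit order, or whether ET values count. Only the visit-order reading loses the ET score and leaves some MITT subjects without a Week 22/LOCF value.

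The sizes are illustrations: 1 to 3 early terminators per cohort of 12 and differences of 3 to 6 points are assumed, giving 0.25 to 1.5 points on the Week 22/LOCF mean against an MCID of 3. The consequence is moderate, because the study is open-label and descriptive, observed Week 22 is shown beside the imputed result, and study day appears in the listings. It should still be corrected: one early terminator is 1/12, about 8%, of a cohort, and the rule bears on the primary variable.

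**What to change.** In SAP 6.2, assign ET and unscheduled assessments to the nearest scheduled visit by actual study day. Let a scheduled value take precedence when both fall in one window. Use Week 28 only for values that fall in its window.

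In SAP 5.1, state that LOCF uses the latest post-baseline UCT by date on or before the Week 10 or Week 22 target window, that ET values count, and that later values are never carried back.

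The cost is about one SAP paragraph and a small derivation. Assessment dates are already collected and study day is already defined in SAP Section 4. Nearest-visit assignment is one convention among several; what matters is that one is written down and that it works by date.
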